Section 8.1, 8.2	The following events were moved from the Withdrawal From Study section to the Discontinuation of Study Treatment section: Pneumonia Acute Respiratory Acidosis/invasive mechanical ventilation Significant changes to ECG, Vital signs, Lab tests. Pregnancy	None of these events require withdrawal from study. Participants that discontinue IP due to these events may remain in the study.
Section 9.2.1	Time period for collection of SAEs has been adjusted to only collect SAEs between ICF and start of study treatment if they are assessed to be related to study participation, or related to a GSK product.	Collection of ALL SAEs between the signing of ICF and start of study treatment was agreed to be unnecessary. The requirement has reverted to the GSK standard for the time period for collection of SAEs.
SoA, Section 8.1	Study flow adjusted so that participants that discontinue	Adjusted in recognition of the fact that 12 weeks of post

Section # and Name	Description of Change	Brief Rationale
	study treatment move directly into the 12-week post treatment follow up period rather than continuing for the remainder of the 12-week treatment period.	treatment follow up is sufficient for participants who discontinue study treatment.
Synopsis, Overall Design, Section 3.1, 5.1, 5.5, 7.1	Clarification provided that dosing at V2 can be performed up to 3pm, extended from 12midday in the previous protocol.	Extended in recognition that there a large number of assessments to be performed and Visits 1 and 2 prior to dosing. Accumulation of drug is observed in the repeat dose pharmacokinetics of nemiralisib of approximately at least 2-fold and therefore dosing up until 3:00 pm on Day 1 does not pose a risk of overdosing on Day 2 when the Day 2 dose is administered in the morning (as early as 6:00 am [i.e., approximately 15 hours after the previous day's dose])
Section 6.2, Exclusion 9, Section 9	Exclusion 9 clarified to allow randomisation ahead of receipt of virology results, with participants to be withdrawn if subsequently found to be positive. Other sections updated to further explain this	Turnaround time of virology is greater than the 48h screening window
Synopsis, Study Rationale, Section 5.1, 7.1	Start of SoC was defined	This was not clear previously

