Participants will be permitted to continue taking inhaled maintenance COPD medications (e.g., long-acting bronchodilators, long-acting beta₂-agonist/corticosteroid combinations, long-acting muscarinic antagonist/long-acting bronchodilator combinations, etc.). Study-supplied rescue medication (albuterol [salbutamol] metered-dose inhaler [MDI] or nebulas) for treatment of acute symptoms of COPD will also be permitted. Other concomitant medications, may be allowed at the discretion of the GSK Medical Monitor and/or Investigator

Participants will then dose at home each morning until Day 84 (– 4 / + 3 days), with the exception of the days when participants come to the clinic. On those days, they will dose at the clinic.

During the 12-week Treatment Period, participants will return to the clinic on an outpatient basis for Visits 3-6 on Study Days 14 (± 3 day), 28 (± 3 days), 56 (– 4 / + 3 days) and 84 (– 4 / + 3 days) to complete the assessments described in the Schedule of Assessments.

Participants who withdraw from the study before completing the 12-week Treatment Period will be asked to return to the clinic within 24 hours (or as soon as possible) for end of treatment assessments (Early Withdrawal Visit).

If a participant is withdrawn from study treatment, he/she will continue existing maintenance COPD therapy or will be prescribed appropriate treatment for COPD and will move directly to the 12-Week Post-Treatment Follow-Up Period for collection of data starting with Visit 7, 28 days after the discontinuation of study treatment.

12-Week Post-Treatment Follow-up Period: The 12-week period following the last dose of double-blind study treatment.

During the 12-week Post-Treatment Follow-Up Period, participants will return to the clinic on an outpatient basis for Visits 7-9 on Study Days 112 (– 4 / + 3 days), 140 (– 4 / + 3 days), and 168 (– 4 / + 3 days) to complete the assessments described in the Schedule of Assessments.

Participants who withdraw from the study before completing the 12-week Post-Treatment Follow-Up Period will be asked to return to the clinic within 24 hours (or as soon as possible) for end of study assessments (Early Withdrawal Visit).

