Laboratory assessments (including hematology and biochemistry) ⁶	X			X ⁸	
Urine pregnancy test (only WOCBP)	X ⁹			X ⁸	

Procedure	Post-Treatment Follow-Up Period				
	Visit	7	8	9	Early Withdrawal
	Day	Study Day 112 ¹⁰ (Day 28 of the Follow-Up Period)	Study Day 140 ¹⁰ (Day 56 of the Follow-Up Period)	Study Day 168 ¹⁰ (Day 84 of the Follow-Up Period)	
	Visit window	- 4/+3 days	- 4/+3 days	- 4/+3 days	
OTHER					
Review smoking status	X	X	X	X	
Smoking cessation counselling	X	X	X	X	
Health Care Resource Utilization (HCRU) Review	< =====>				

CAT=COPD Assessment Test; EXACT=EXAcerbations of Chronic Pulmonary Disease Tool; FEV₁=forced expiratory volume in one second; IRT=Interactive Response Technology; WOCBP=women of child-bearing potential

1. Completed daily in the evening
2. Subjects should complete the CAT at the visits noted as well as 7 days post EXACT-defined day of recovery after exacerbation; the CAT will be completed prior to the SGRQ-C and other study assessments/procedures
3. Subjects should complete the SGRQ-C after completing the CAT and prior to other study assessments/procedures
4. Performed prior to dosing of concurrent COPD treatment(s) and pre-bronchodilator and post-bronchodilator (approximately 10 to 30 minutes following treatment with albuterol [salbutamol], administered as either four inhalations via the metered-dose inhaler [MDI] (i.e., 400 mcg) with valved-holding chamber or one nebulized treatment)
5. Daily recording via the clip-on Propeller Sensor for MDI and via the eDiary (for countries where the Propeller Sensor for MDI is available) or via the eDiary only (for countries where the Propeller Sensor for MDI is not available or if nebulized albuterol [salbutamol] is used)
6. Prior to dosing of concurrent COPD medication(s)
7. Single assessment
8. Procedure completed only if the Early Withdrawal Visit occurs prior to Day 112
9. If the urine pregnancy text result is positive, a blood sample for serum pregnancy testing will need to be conducted to confirm pregnancy status
10. Participants who discontinue from study treatment will move directly into the 12-Week Post Treatment Follow Up Period starting with Visit 7. Visits for these participants will not align to Day 112, 140, 168, rather will occur every 28 weeks following the study treatment discontinuation date.

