3.3.1. Risk Assessment

Potential Risk of Clinical Significance	Summary of Data/Rationale for Risk	Mitigation Strategy
Investigational Product (IP): Nemiralisib		
Bronchospasm	Inhaled treatment	Participants will be allowed to continue regular COPD treatments and have SoC. More severe participants will have their treatment started in hospital.
Mucosal irritancy	Detected in 13-week toxicology study in the dog	Participants will be regularly monitored for AEs and a participant eDiary kept. Thus far, mucosal irritancy has not been observed in clinical studies.
Post-inhalation cough immediately following inhalation of study treatment (nemiralisib)	In the Proof-of-Concept (PoC) study PII116678, which was conducted in 126 randomized participants from a population similar to this protocol and a previous formulation of nemiralisib (DISKUS formulation blended with only one excipient, lactose), there was a higher incidence of treatment-related, mild and moderate adverse events of cough (Preferred Term) reported immediately after dosing in exacerbating subjects in the nemiralisib DISKUS 1000 mcg QD group (n=22 [35%] compared exacerbating subjects in the placebo DISKUS group (n=2 [3%]). For the 22 subjects in the nemiralisib 1000 mcg group, the events for 20 of the subjects were considered by the Investigator to be related to study treatment. From the review of reported terms, cough often occurred	
To further evaluate this finding of post-inhalation cough immediately following dosing, during study Visits 2-6 in the 12-Week Double-Blind Treatment Period, Investigators (or medically qualified designees) will observe participants for post-inhalation cough within 5 minutes immediately following dosing. If coughing is observed, details will be recorded in the source documentation and in the eDiary/eCRF.
 
In addition, outside of the clinic visits, participants will have the opportunity to report post-inhalation cough (as well as other changes in medical conditions/changes in medications) in the eDiary, which will be reviewed by the Investigator/medically qualified designee for reporting of any AEs/SAEs (See Section 9.2).

Potential Risk of Clinical Significance	Summary of Data/Rationale for Risk	Mitigation Strategy

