8.1. Discontinuation of Study Treatment

A participant may be discontinued from study treatment but continue in the study for collection of data (including efficacy and safety data) and to minimize missing data. Participants who discontinue from study treatment will move directly into the 12-Week Post Treatment Follow Up Period starting with Visit 7, 28 days following the discontinuation date.

[figure not shown]
If a higher than expected number of participants prematurely discontinues double-blind study treatment or prematurely discontinues from the study, additional participants may be randomized, at the discretion of the Sponsor.

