10.1. Sample Size Determination

The sample size has been determined by considering the probability of achieving the end of study success criteria for both the primary and key secondary objectives.

Assuming a 20% withdrawal rate, approximately 1,250 participants will be randomized in total into the study to ensure approximately 1,000 participants complete the 12-Week Treatment Period.

Initially, the randomization ratio between placebo and the the six doses (12.5 mcg, 50 mcg, 100 mcg, 250 mcg, 500 mcg, and 750mcg) of nemiralisib will be 3:1:1:1:1:3. Randomization will be stratified by index COPD exacerbation severity (moderate or severe) and whether or not the participant will provide PK samples, to ensure a balance across treatments. [Table 2](#) shows the expected sample sizes allocated to the six doses of nemiralisib and placebo at the end of study. These figures are approximate and assume that no further adjustments to the randomization ratio are made. The actual sample sizes at the end of the study may be different, depending upon whether changes are made following the results of the unblinded interim analysis of change from baseline in clinic visit FEV₁.

Table 2 Expected Sample Sizes Allocated to the Five Doses of Nemiralisib and Placebo at the End of the Study

Dose	Number randomized	Number who complete dosing period and provide clinic visit FEV ₁ at Day 84
Placebo	340	272
12.5 mcg	114	91
50 mcg	114	91
100 mcg	114	91
250 mcg	114	91
500 mcg	114	91
750 mcg	340	272

10.1.1. Sample Size for Primary Objective: To Characterize the Dose Response of Nemiralisib when Administered in Addition to SoC on Change from Baseline in Clinic Visit FEV₁ at Day 84

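### Participants who stop study treatment but stay in the study have no scheduled Day 84 spirometry, the only time point in the stated primary model

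*Protocol*

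**What the plan says.** Section 8.1 allows a participant to stop study treatment and "continue in the study for collection of data (including efficacy and safety data) and to minimize missing data". The next sentence sets the flow: "Participants who discontinue from study treatment will move directly into the 12-Week Post Treatment Follow Up Period starting with Visit 7", 28 days after stopping. The synopsis says the same. Footnote 10 to the follow-up Schedule of Activities reads "Visits for these participants will not align to Day 112, 140, 168, rather will occur every 28 weeks following the study treatment discontinuation date". The Amendment 02 summary shows that the change was deliberate: participants that discontinue "study treatment move directly into the 12-week post treatment follow up period rather than continuing for the remainder of the 12-week treatment period".

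The Early Withdrawal Visit is worded for leaving the study, not for stopping treatment: "Participants who withdraw from the study before completing the 12-week Treatment Period will be asked to return to the clinic within 24 hours". It takes place at withdrawal, not at Day 84.

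The primary endpoint is the change from baseline in post-bronchodilator trough FEV1 at Day 84 (Section 4). The Emax model in Section 10.3.1 is written for that one value, with dose as the only regressor. Table 2 in Section 10.1 counts evaluable participants under the heading "Number who complete dosing period and provide clinic visit" FEV1 at Day 84, and the simulations in Section 10.1.1 use those counts. Section 10.2 assigns all efficacy summaries to MITT, meaning everyone randomized and dosed. Section 10.3.5 uses the same Day 84 endpoint for interim changes to the allocation. Section 10.3.1 leaves the full details of the analysis to the RAP.

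**The concern.** These participants still consent, still attend and still perform spirometry, but not on the day the primary endpoint needs. A data-collection rule in the protocol creates this gap, and no analysis plan can recover a value that was never measured.

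The follow-up spirometry does not fill the gap as the endpoints are defined. The follow-up FEV1 endpoint is the change from Day 84 to Days 112, 140 and 168. Someone who stopped early will usually lack the Day 84 reference, and their visits do not fall on those days.

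Stopping is unlikely to be unrelated to outcome. Pneumonia, respiratory acidosis or invasive ventilation, and newly started CPAP or NIPPV all require it (Sections 8.1.3, 8.1.4 and 7.7.1.2). It may also differ between arms. In the proof-of-concept study "there was a higher incidence of treatment-related, mild and moderate adverse events of cough" on active drug (35% versus 3%), and all three participants who discontinued for cough were on drug. If stopping differs by arm and those who stop have different FEV1, the Day 84 contrast no longer compares the groups as randomized. The interim decisions to drop, add or re-weight doses would use the same selected data.

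**Working it through.** **1. The plan's own numbers.** 1,000 / (1 − 0.20) = 1,250. By arm, 340 × 0.8 = 272 and 114 × 0.8 = 91.2, shown as 91. The Table 2 columns sum to 1,250 and 999. The sample size reproduces and already allows for about 250 MITT participants without a Day 84 value: 68 in each large arm and 23 in each small arm.

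**2. How many this rule affects.** The 20% is a withdrawal rate. It is not split between leaving the study, where Day 84 is lost under any schedule, and stopping treatment while staying. Only the second group is affected, so the number is anywhere from 0 to 250.

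**3. When Day 84 would be caught by chance.** Take the 28-day reading, with nominal visits at stop day + 28, + 56 and + 84. The Visit 6 window (−4/+3) is Days 80 to 87. A follow-up visit falls in it for stops on Days 52–59 (+28), 24–31 (+56) or 1–3 (+84). That is 8 + 8 + 3 = 19 of the 79 possible stop days before the window opens. Even then the visit is not Visit 6, and the protocol states no primary-analysis use for it.

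**4. Precision.** Section 10.1.1 gives SD 300 mL at both times and correlation 0.7. The SD of the change is 300 × √(2 × (1 − 0.7)) = 232.4 mL. The SE for 750 mcg versus placebo is 232.4 × √(2/272) = 19.9 mL.

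**5. Illustrative bias (rates and deficit are assumed).** Let those who stop have a mean change lower by d than those who continue, with the same d in both arms, and let p be the proportion stopping. Each all-randomized mean is then the continuers' mean minus p × d. So:

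continuers' contrast − all-randomized contrast = (p on drug − p on placebo) × d

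| Stopping, drug vs placebo | d = 50 mL | d = 150 mL |
|---|---|---|
| 20% vs 20% | 0 mL | 0 mL |
| 22% vs 18% | 2 mL | 6 mL |
| 25% vs 15% | 5 mL | 15 mL |
| 30% vs 10% | 10 mL | 30 mL |

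**6. Effect of including off-treatment values.** Table 3 implies 750 mcg minus placebo of 100, 70 and 20 mL in scenarios 1 to 3. Assume that 20% stop, all stay in the study and all lose the whole benefit. The all-randomized effect is then 0.8 × these: 80, 56 and 16 mL, which is 20, 14 and 4 mL below the continuers' effect.

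A re-simulation with a 3-parameter Emax fit, 5,000 trials per scenario, gave these probabilities for the third criterion of Table 4 (posterior probability above 90% and observed difference above 75 mL):

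| | Scenario 1 | Scenario 2 | Scenario 3 |
|---|---|---|---|
| Table 4 as stated | 97% | 44% | 0% |
| Re-simulated, Table 2 completers | 96% | 44% | 0% |
| Re-simulated, all 1,250, diluted effect | 74% | 14% | 0% |

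This approximate fit did not reproduce the first row of Table 4 (94–99% against 53%, 62% and 88%). In the second row it gave 56–61% for scenario 3 against 64% stated. Neither figure bears on this point.

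**The case against.** The strongest counter-argument is that the flow was chosen deliberately in Amendment 02, and that an on-treatment dose-response is a legitimate target in Phase IIb, which off-treatment values would dilute. Step 6 shows that the dilution could be large. This bears on which contrast to report, not on whether to take the measurement: a Day 84 value can be used or set aside, but a missing one leaves no choice.

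Second, nearby data exist. On the 28-day reading, any stop up to about Day 70 gives spirometry within 14 days of Day 84 if follow-up is attended. Section 10.3.4 also plans a longitudinal FEV1 model over all time points. Both facts stand and reduce the harm. That model is described only as additional support, however, and nearby values need modelling assumptions that a Day 84 visit would avoid.

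Three stronger readings are tempting, and the protocol supports none of them.

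- **That 250 participants lose the endpoint because of Section 8.1.** That figure is the total planned attrition.
- **That the primary analysis is defined as a completers analysis.** Table 2 is a sample-size table, Section 10.2 names MITT, and the RAP, which is not shown, may specify a repeated-measures model or other handling of missing data.
- **That the bias is known to favour drug, most of all at 750 mcg.** The proof-of-concept study used 1000 mcg in an earlier DISKUS formulation. Its three cough discontinuations among about 22 / 0.35 = 63 on drug are roughly 5% versus 0%, which by the formula in step 5 gives about 2 to 7 mL. Nothing shows that those who stop for cough have worse FEV1. If the drug reduces infections, pneumonia stops could be more common on placebo and the bias could reverse.

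**Conclusion.** The point holds as a scheduling defect. Section 8.1, the synopsis and footnote 10 agree that a participant who stops treatment but stays in the study is not scheduled for Day 84 FEV1. This contradicts Section 8.1's stated purpose and cannot be repaired later. As the protocol states them, the primary and interim fits rest largely on participants still on treatment at Day 84.

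The size is not known. The number affected lies between 0 and 250, and the direction of bias cannot be derived from the protocol. The moderate illustrations (2–6 and 5–15 mL) stay below one standard error of 19.9 mL; only the widest assumed imbalance, 30% versus 10%, reaches beyond it. The case for acting is that the loss is irrecoverable and cheap to prevent, not that a large bias has been shown.

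**What to change.** **Data collection.** In Section 8.1, the synopsis and footnote 10 of the follow-up Schedule of Activities, have participants who stop treatment but remain in the study attend pre- and post-bronchodilator spirometry at Day 84 (−4/+3) counted from randomization, by re-timing or adding one follow-up visit. Flag each value as on or off treatment.

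**Visit interval.** Footnote 10 gives 28 weeks between visits after stopping, while Section 8.1 and the synopsis place Visit 7 at 28 days. These must be reconciled in the same edit.

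**Analysis.** In Section 10.3.1, state that Day 84 values are analysed for MITT regardless of treatment status and that FEV1 already collected at Days 14, 28 and 56 is used, for example in a repeated-measures dose-response model. Report the on-treatment (completer) fit alongside. If the RAP already says this, a cross-reference is enough.

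**Cost.** One moved or extra spirometry visit for those who stop, and some more modelling. The Day 84 estimate would include off-treatment values and could be noticeably smaller, for example 80 instead of 100 mL in scenario 1 under the assumptions of step 6. The probabilities in Table 4 should be re-examined for whichever contrast is made primary.

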8.1.1. Liver Chemistry Stopping and Follow-up Criteria

Liver chemistry stopping and increased monitoring criteria have been designed to assure participant safety and evaluate liver event etiology (in alignment with the FDA premarketing clinical liver safety guidance). These protocol guidelines are in alignment with FDA premarketing clinical liver safety guidance:
<http://www.fda.gov/downloads/Drugs/GuidanceComplianceRegulatoryInformation/Guidances/UCM174090.pdf>.

Discontinuation of study treatment for abnormal liver tests is required when:

- a participant meets one of the conditions outlined in the algorithm below
- in the presence of abnormal liver chemistries not meeting protocol-specified stopping rules, the investigator believes study treatment discontinuation is in the best interest of the participant.

Figure 2 Liver Chemistry Stopping and Increased Monitoring Algorithm

Refer to [Appendix 7](#) for required Liver Safety Actions and Follow-Up Assessments.

8.1.2. QTc Stopping Criteria

In this study, GSK is contracting with an external vendor to provide standardized 12-lead ECG equipment and centralized ECG overreads for all participating sites (Section 9.4.3).

The same QT correction formula (Fridericia's) *must* be used throughout the study for all participants. Safety ECGs and other non-protocol specified ECGs are an exception.

The QTc criteria should be based on the averaged QTc value of triplicate ECGs obtained over a brief (e.g., 5-10 minute) recording period.

A participant who meets either bulleted criteria based on the average of triplicate ECG readings will be withdrawn from study treatment:

- QTc >530 msec (with or without underlying Bundle Branch Block) OR Uncorrected QT >600 msec
- Change from baseline of QTc > 60 msec

In addition, participants should be excluded (Screening) or be discontinued from study treatment if they have an abnormal, clinically significant ECG finding as defined in the ECG manual.

8.1.3. Pneumonia

Presumptive diagnosis or radiographically confirmed (See definition in “COPD Exacerbation” Section 9.1.2) requires discontinuation of study treatment.

If a subject is withdrawn due to pneumonia, the AE/SAE section and the pneumonia/chest X-ray section, if applicable, of the eCRF should be completed and the subject should be followed until clinical resolution of the pneumonia.

8.1.4. Acute respiratory acidosis/invasive mechanical ventilation

A pH < 7.30 or the need for invasive mechanical ventilation requires discontinuation of study treatment.

8.1.5. Other Safety Stopping Criteria

For a study participant, other safety stopping criteria include, but are not limited to:

Severe signs or symptoms or significant changes in any of the safety assessments, that put the safety of the participant at risk (e.g. ECG, vital signs, laboratory test, etc.), as judged by the Investigator, in consultation with the Medical Monitor if necessary.

